rates, problem solving issues relating to attrition as they arise. The best solution to missing data is to avoid it, or at least minimise its occurrence. However, in a cohort with first episode psychosis, it is unlikely that there will be no missing data. We will, therefore, assess the robustness of our findings to any missing data, using multiple imputation techniques (assuming data are missing at random) and if the level of missing data warrants it, models assuming informative missingness (e.g. pattern mixture models) following relevant guidelines (27). We will however be restricted in this feasibility stage by the small sample sizes (~30 in each randomised arm).

Data collection:

Acceptability of treatment will be measured using drop-out rates, and explored in detail using qualitative methods. Therapeutic improvement will be assessed in terms of rate and degree of recovery from psychosis symptoms, age appropriate functioning and overall health status and utility. Assessors blind to randomised group will conduct all assessments at baseline and at 3, 6 and 12 months' post-randomisation. We propose a variable follow-up, with CYP recruited after 10 months being offered assessments only to end of treatment (6 months). Thus, participants recruited in the first 10 months will receive the full 12–month follow up, whereas participants recruited thereafter would be offered assessments up to the end of treatment (6 months, our primary end point).

We will assess the possibility for economies of scale throughout the trial and we will monitor time use of the research assistants via their regular contact with the trial manager. This will include monitoring of diary appointments, proportions of cancelled and not attended appointments, enquiry to referral and referral to randomisation ratios. We will also collect routine data from the participants' medical records in order to explore the scope for utilising such data in a future definitive trial. We will compare the data collected by our research team to the routine service data to identify any potential for savings (i.e. for reducing the participant burden and required research assistant resources at each site).

Primary outcome:

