As this is a feasibility trial, a single primary outcome is not meaningful and the key outcomes to inform a future trial are referral rates, recruitment, attendance at therapy sessions, compliance with medication and follow-up and questionnaire response rates. Acceptability of treatment will be measured using rates of drop-out from treatment.

Secondary outcomes:

All secondary outcomes are being collected to determine their suitability for use in a subsequent trial, rather than to draw conclusions about safety or efficacy of treatments.

The proposed primary outcome measure for a subsequent definitive trial will be total PANSS score (4), a commonly used outcome in psychosis trials, allowing comparison with wider evidence. The PANSS is a 30-item rating scale designed to provide a comprehensive assessment of psychopathology in adults with a diagnosis of schizophrenia. Five components have been reported: positive, negative, depression-anxiety, agitation-excitement, and disorganisation.

In order to test the acceptability and usefulness of potential secondary outcome measures in a trial context, we will also assess: i) social/educational/occupational functioning ii) self-rated

recovery iii) dimensions of psychotic symptoms. Adverse effects (weight gain, sexual dysfunction, metabolic effects and extrapyramidal effects) will be systematically assessed. Hospital admissions, serious adverse events and dose of APs and PIs will also be measured in all groups

Social/educational/occupational functioning

Social and educational/occupational functioning will be assessed using the First Episode Social Functioning Scale (FESFS) (28). The FESFS was developed with over 200 individuals receiving services in first episode psychosis clinics. Subscales include: Friendships and social activities, Independent living skills, Interacting with people, Family, Intimacy, Relationships and social activities at work, Work abilities, Relationships and social activities at school, Educational abilities. This measure has good reliability, convergent and discriminant validity and sensitivity to change. We will also assess time use in constructive economic activity.

Recovery

Recovery will be assessed using the questionnaire about the process of recovery, a user-defined measure (QPR (29)), which is a 15-item questionnaire developed collaboratively with service users with psychosis, measuring subjective recovery.

Dimensions of Psychotic Experiences

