Intervention and trial acceptability: Qualitative interviews

A nested qualitative study will identify key themes associated with the acceptability of the trial and interventions amongst CYP, carers and clinicians. Individual semi-structured interviews will explore participants' experience of recruitment, random allocation and receiving interventions and identify barriers and solutions to participation, by focusing on e.g. structural issues (access/choice/amenities); process (personalisation, interpersonal quality of care, co-ordination of care) and outcomes (perceived mental and physical well-being). This phase will explore the subjective experience of receiving the treatments, elicit service user views of adverse effects and benefits, and identify themes relating to these issues. Similar interviews will be undertaken with parents and clinicians. As MAPS is a multi-site trial the participants, family members/carers and clinicians will be offered the choice of completing a qualitative interview over the telephone if they wish. The option of a telephone interview would maximise opportunities for participants to take part and capture the views of hard-toreach participants and their family members/carers as demonstrated by other published qualitative studies [40]. As the MAPS trial is multi-site, participants are geographically dispersed and the qualitative research assistant (RA) is based in Manchester, our interview approach needs to be flexible and offer potential interviewees the choice of a face-to-face or a telephone interview. Telephone interviews have been found to be comparable in quality to face-to-face interviews [41].

Prior to a telephone qualitative interview with a research participant from the main trial, the qualitative RA would conduct a thorough check of risk with the participants care coordinator and with the trial therapist (if allocated to a therapy arm) and establish a clear plan for contingencies if required (access to immediate local info for support and referral access). Participant qualitative interviews are conducted after the 6 month follow-up assessment with the MAPS trial RA and so by 6 months it is reasonable to assume that the participant is well known to the trial including any potential risks. We would offer all trial participants and family members who take part in the qualitative interview the option of a 24-hour-later follow-up call (per previous studies)

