This will inform the design of a definitive trial and help further refine intervention, recruitment and retention procedures. Semi-structured interviews will be conducted after 6 month assessments. We will seek a maximum variance sample on key variables (engagement with interventions, symptoms, site, age and gender). These interviews will be conducted with participants allocated to each arm of the trial after completion; this will allow us to explore people's experiences of receiving the treatments. Based on our previous work it is expected that thematic saturation will be achieved with 15-20 CYP (38), 15-20 carers (39) and 15-20 clinicians. All interviews will be audio-recorded and transcribed verbatim. Data will be analysed using thematic analysis (42), which results in a rich and accessible account of qualitative data. The researcher makes sense of the data and reports themes that emerge (42). We will assume a realist perspective and report the experiences of participants. Themes will be coded inductively at a manifest level to inform the design of the definitive trial and refine the therapy protocol. The interviews will be overseen by service user researchers who have a wealth of experience of such qualitative research; transcripts will be reviewed and coded by our service user researchers with input from our service user reference group. Coding will be conducted systematically and iteratively and organised within NVivo.

We will also attempt to capture relevant data from people who decline to participate in the trial (young people, parents and clinicians), either using interview methods or a self-report questionnaire. This will further inform the design of a definitive trial and help further refine intervention, recruitment and retention procedures.

Assessments of moderation and mediation

In order to inform a definitive trial design and analysis plan, we will also address the influence of compliance via causal or 'mediation' models (statistical lead: [name]). Traditional approaches to mediation (43) assume that confounding between the putative mediator and clinical outcome is absent (i.e. there is no omitted variable bias). We will compare the results of three sets of assumptions: (a) no confounding, (b) that we have measured and are able to adjust for all important confounders (44), and (c) that we are able to effectively adjust for

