The first 6 weeks (study set up period): The study will begin when the RAs are recruited in each centre. The process of publicising the study will continue. Therapy procedures and the procedures for optimal treatment as usual will be finalised. Training will be provided for therapists in delivering the intervention. Training will be provided for the RAs in undertaking assessments until reliability is established. An intensive, residential training programme will be delivered in month 1.

Study recruitment (Months 2 to 16): In month 2, recruitment to the feasibility study will begin in teams at each site. Randomisation will follow gaining informed consent and an initial interview to determine participant eligibility. Recruitment will continue for 15 months and participants will be followed up at 3, 6 and 12 months. Qualitative interviews will commence in month 6 with clinician interviews.

Study follow up assessments (months 5 to 22): Trial follow up assessments will end in month 22. Qualitative interviews with participants and parents will be undertaken after end of treatment assessment has occurred (6 month assessments), from month 7 onwards.

Decision making and preliminary trial write up: (months 23 to 24): In months 23-24 we will present to the HTA data on recruitment and retention in the trial in order to obtain ratification of the recommendations of the TSC and DMC.

Project management

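### The protocol gives no interview route for young people who withdraw from assessments or are lost before the 6-month visit, or for their parents, although the interviews are meant to help improve retention

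*Protocol*

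**What the plan says.** The protocol places the participant interviews relative to the 6-month assessment in three places.

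- Plan of investigation and timetable, Study follow up assessments: "Qualitative interviews with participants and parents will be undertaken after end of treatment assessment has occurred". This covers parents as well as young people.
- Intervention and trial acceptability: Qualitative interviews, in the text on telephone interviews and risk: "Participant qualitative interviews are conducted after the 6 month follow-up assessment with the MAPS trial RA".
- The same section, on sampling: "Semi-structured interviews will be conducted after 6 month assessments", and then "These interviews will be conducted with participants allocated to each arm of the trial after completion".

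The sampling variables are listed there too: "We will seek a maximum variance sample on key variables (engagement with interventions, symptoms, site, age and gender". Retention status is not among them. A separate route is described for people outside the trial: "We will also attempt to capture relevant data from people who decline to participate in the trial (young people, parents and clinicians".

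On purpose, Data collection states: "Acceptability of treatment will be measured using drop-out rates, and explored in detail using qualitative methods". The Primary outcome section is more specific: "Acceptability of treatment will be measured using rates of drop-out from treatment". The qualitative section adds that the interviews should help to improve the intervention, recruitment and retention for a definitive trial.

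**The concern.** The rationale names retention as one of the key uncertainties, the objectives include the drop-out rate, and the success criteria make the proportion assessed at 6 months one of four tests for progression. If retention falls short, the steering and monitoring committees will want to know why young people left and what might have kept them.

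The people best placed to say are those who left before 6 months, and their parents. A rule that holds the interview until after the 6-month assessment misses that group. Their accounts cannot be recovered once the trial has closed.

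**Working it through.** The protocol states no figure on this point to reproduce. The check is a reading of the text, followed by simple counts.

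**1. Time point or completed visit?** The general sampling sentence could mean only that interviews happen from about 6 months. The other statements point to a visit that took place. The timetable says the assessment has occurred, the telephone text refers to the assessment with the trial research assistant, and the sampling text adds that completion comes first. The stricter reading is the more natural one. No sentence expressly bars anyone; the gap follows from the timing.

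**2. Does another route reach those lost before 6 months?**

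| Route | Reaches them first-hand? |
|---|---|
| Interviews with people who decline the trial | No. It concerns people who never joined. |
| Sampling on engagement with interventions | Only if they attend at 6 months. |
| Clinician interviews from month 6 | No. Second-hand at best. |
| Procedure on withdrawal (Assessments section) | No. It asks only about a thank-you card. |

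**3. Who is not affected?**

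- Those who stop treatment but stay in follow-up. Concomitant therapy commits to following all randomised participants whatever they receive, and engagement is a sampling variable.
- Those who leave between 6 and 12 months. They have already reached the interview point.

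**4. How many are affected?** Inputs: 90 randomised (Sampling and Feasibility of recruitment); a green limit of 80% retention at 6 months, with 60% as the foot of the next band (Measurement of feasibility success criteria); attrition under 10% in another trial by the same group (Minimising attrition). Number without a 6-month assessment = 90 × (1 − retention).

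- Retention 90%: 90 × 0.10 = 9. Since the quoted attrition is below 10%, this is an upper figure.
- Retention 80%: 90 × 0.20 = 18.
- Retention 60%: 90 × 0.40 = 36.

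These count young people with no described route, not interviews lost. Only 15–20 young people are to be interviewed. At 20% loss, a proportionate share of those places would be 15 × 0.20 = 3 to 20 × 0.20 = 4.

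**The case against.** The strongest reply is that the protocol measures acceptability by drop-out from treatment, not by loss to the trial. Someone who gives up tablets or therapy in the first weeks is still due a 6-month assessment and can be interviewed after it, and the sampling plan seeks out variation in engagement. This stands. A reader might infer that everyone who drops out is shut out and that the acceptability findings will come from stayers only. The documents do not support that.

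It can also be said that a timing statement is not an eligibility rule, and that clinician interviews may shed light on why patients left. Both are fair, but neither fills the gap. A team that follows the stated order would have no basis for approaching a person who has no 6-month assessment, and a clinician's view is not the young person's or the parent's.

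The timing has good reasons behind it. By 6 months the participant and any risks are known to the trial, and Protection against bias limits contact within the treatment window to protect the blind. An interview triggered merely by stopping treatment could come before the blinded 6-month assessment and might prompt disclosure of allocation or affect later self-report. That argues against a treatment-stop trigger. It does not argue against interviewing people who have left assessments or whose 6-month visit has been missed, because no 6-month rating remains to be protected.

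Finally, some of those lost will have withdrawn consent or be unreachable, and no change of timing recovers them. This is true, and it makes the counts upper limits.

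**Conclusion.** The point holds in a limited form. The protocol ties the participant and parent interviews to a 6-month assessment that has taken place, and it describes no interview route for randomised young people who withdraw from assessments or are lost before it, or for their parents. The interviews are therefore likely to miss first-hand accounts from those who fail the 6-month retention criterion: up to 18 of 90 at the green limit, or about 9 of 90 at the attrition seen in the group's other trial.

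This rests on the stricter reading of the timing statements and on full recruitment of 90. The effect on what is learned about retention is direct. The effect on acceptability is only partial, because treatment drop-outs who attend at 6 months remain within reach. A reader might conclude that the qualitative findings will be too favourable. That is possible but not shown, since the sampling aims at range of experience rather than representativeness. No quantitative outcome is harmed. The change is still worth making, because it is cheap and the missing accounts cannot be obtained later.

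**What to change.** Keep the present timing for everyone still in follow-up, so that no interview comes before their blinded 6-month outcome.

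Amend the three timing statements so that two further groups, and their parents, may also be interviewed:

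- young people who withdraw from assessments, from the date of withdrawal;
- young people whose 6-month visit is missed, once the window for that visit has closed.

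Interviews would be done by the qualitative research assistant, by telephone if preferred. They would take place only where consent has not been withdrawn, and subject to the risk check with the care coordinator (and the trial therapist, where there is one) and the re-confirmation of consent already described in the qualitative section. Parents would follow the existing family-member consent procedure.

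Add retention status to the maximum-variance sampling variables, within the existing 15–20 young people and 15–20 carers.

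The cost is a short wording amendment. Staff, telephone option, consent at trial entry and interview numbers stay as they are. The downside is that some of those approached will refuse, and a few interviews will take more effort to arrange.
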